Inclusion Criteria:	 Individuals who meet all of the following criteria are eligible to participate in the study: Age between 18 and 65 years, inclusive. Body weight >45 kg. Body Mass Index >18.5. Close contact with a person who has a PCR-confirmed SARS-CoV-2 infection within 5 days before screening. Only one member in the same household will be enrolled. Participants must be able to give informed consent and comply with the study's scheduled events/visits and study assessments. SARS-CoV-2 positive index case must be able to give consent to enable collection of the documented positive PCR test. Female participants of childbearing potential must use a highly effective method of contraception for the duration of the trial. Their male partners should also use a contraception method (i.e condom) unless vasectomized. (Refer to section 4.5 Contraception Requirements). Male participants must use a contraception method (i.e condom) for the duration of the trial, unless vasectomized. Their female partners, if they are of childbearing potential, must use a highly effective method of contraception. (Refer to section 4.5 Contraception Requirements). 			

Exclusion Criteria:	Individuals who meet any of the following criteria are not eligible to			
	participate in the study:			
	1. Pregnant or breast-feeding.			
	2. Participants who have been administered COVID-19 vaccine			
	prior to the inclusion or have a planned vaccination during			
	the duration of the study.			
	3. A positive COVID-19 result (PCR or antigen test) within 8 days of screening.			
	4. Presence of typical COVID-19 symptoms (fever >38°C,			
	SpO2 below 93%, dyspnoea, difficulty breathing, chills,			
	repeated shaking with chills, ageusia, anosmia, cough,			
	myalgia, headache) in the past 48 hours prior to screening.			
	5. Presence of a known uncontrolled/unstable clinically			
	significant medical condition, considered by the investigator			
	as incompatible with study participation.			
	6. Known history of HIV, HBV and/or HCV.7. Hypersensitivity to any component of ivermectin.			
	J1 J J 1			
	8. Participants who have been administered ivermectin within 30 days prior to screening.			
	9. Participation in another interventional trial within the last 30			
	days or 5 half-lives of the IMP of the other trial, whichever			
	comes first.			
	10. Having undergone extensive bowel resection which may			
	alter ivermectin absorption.			
	11. Participants with gastrointestinal erosions and ulcers (e.g.			

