- (c) IMP will be administered as follows: 200 µg/kg as the loading dose admisnistered on D1at the study site, and then 100 µg/kg/day for 27 days taken by the participant at home.
- (d) PCR test to be performed on D1, D4, D7, D10 and D28: sequencing and viral load. In addition, any unscheduled test performed by the participant during the study will also be collected. Confirmed negative participants at baseline will continue RT-PCR testing, as per schedule of assessments, until they become positive or reach the planned end of study. When RT-PCR positivity is confirmed, participant will self-isolate according to local requirements.
- (e) Participants who have been tested positive at the screening with a quick antigen test will be screen failed. In addition, any unscheduled test performed by the participant during the study will also be collected,
- (f) Serology COVID-19 (antibodies levels). In addition, any unscheduled test performed by the participant during the study will also be collected).

(g) Haematology, Biochemistry, Urine pregnancy test,	for details on the parameters evaluated. Pregnancy testing must be highly sensitive, at leas
before first administration.	-

- (i) Participants will receive their diary on D1 and keep it for the duration of the treatment to record data collected between D1 and D28. They will bring it back to the site on D28.
- (J) Additional follow-up remote or on-site unscheduled visits, may be required if deemed necessary by the investigator, notably in case of emerging or prolonged adverse events. During the unscheduled visit, the investigator will evaluate the WHO COVID-19 scale and the NEWS-2 scale, in addition to any assessments deemed necessary.

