1.3 Study design

This is a randomised, double blind, parallel-group, placebo-controlled, multicentric Phase II clinical trial evaluating the efficacy and safety of ivermectin tablets in the prevention of COVID-19 infection.

If all eligibility criteria are met, the participant will be randomised, and a loading treatment dose will be administered.

Participants will be assigned in a 1:1 ratio to receive oral daily treatment with either ivermectin or placebo. Randomisation will be performed stratified by country.

The study requires two visits to the study center, on Day 1 and Day 28, the first and last days of treatment. In addition, there will be 3 remote visits (day 4, day 7 and day 10) that can be conducted by telephone.

The treatment period lasts for 28 days in total, followed by a 28-day follow-up period, and there is a 2-day window period for visits. Therefore, total study duration for each participant is up to 58 days.

Ivermectin will be supplied as 3 mg tablets and will be administered orally, under fasting conditions, as follows: 200 ug/kg as the loading dose on Day 1 and then 100 ug/kg/day for

Statistical Analysis Plan	Version 1.0		Page 7 of 25
Sponsor	MedinCell	Protocol No	mdc-TTG-CT-002

27 days. Control participants will receive placebo tablets, the number of tablets to be taken will match the number of IVM tablets taken by the active participants in the same body weight range.

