3.4 Modified Full Analysis Set

Modified FAS (mFAS) includes all FAS participants with a confirmed negative SARS-CoV-2 RT-PCR test at baseline.

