4.1 Conventions

4.1.1 Baseline definition

Results obtained on D1 (Screening/Randomization) of the study are considered as baseline results. In case of more than one result the closest to start of treatment will be used.

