4.6 Efficacy

4.6.1 Primary endpoint

The primary endpoint is the proportion of laboratory-confirmed COVID-19 infections between baseline and Day 28. Frequency tables will be provided, and individual results will be listed.

For missing results of the primary endpoint, the multiple imputation (MI) method will be used. MI is performed using 3 general steps: imputation, analysis, and pooling. A total of 10 multiple imputations will be generated using a fully conditional specification (FCS) regression. This method conditions on observed values of the primary outcome measured at other time points (including baseline measurements) and possible other covariates that are related to the missing data pattern and/or primary endpoint. Furthermore, imputations will be performed in each treatment group separately and, if applicable, by stratification factor. The statistical model will be applied to each imputed dataset separately. The estimated parameters from the models will then be pooled using Rubin's combining rules. It should be noted that these combination rules rely on the assumption that the estimated

Statistical Analysis Plan	Version 1.0		Page 14 of 25
Sponsor	MedinCell	Protocol No	mdc-TTG-CT-002

statistics are approximately normally distributed, which may not be the case for the underlying data. Normalizing transformations will then be used on the estimated statistics prior to applying Rubin's rules.

The comparison between the two treatment groups of the proportion of participants will be performed using the Cochran Mantel Haenszel (CMH) chi-squared test. Odds-ratio, relative risk and risk differences and corresponding 95% CI will be reported. Country will be used as a stratification factor. In case the study was only performed in one country, the Chi-squared/Fisher's exact test will be used.

This analysis will be performed based on the mFAS and PP population using the planned treatment

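### The primary test stratifies by country only; adding Day 1 antibody serostatus, which is already collected, would gain a modest amount of power

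*SAP*

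**What the plan says.** - **Primary test.** SAP 4.6.1 specifies a CMH test: "Country will be used as a stratification factor". This follows SAP 1.3: "Randomisation will be performed stratified by country". For a single-country study, SAP 4.6.1 adds: "In case the study was only performed in one country, the Chi-squared/Fisher's exact test will be used".
- **Serology.** The protocol's Table 1 schedules it on D1, D28 and D56, and footnote (f) describes it as "Serology COVID-19 (antibodies levels". SAP 4.1.1 makes the first sample a baseline value: "Results obtained on D1 (Screening/Randomization) of the study are considered as baseline results".
- **Who can enter.** The protocol synopsis excludes "Participants who have been administered COVID-19 vaccine" before inclusion (criterion 2) and "A positive COVID-19 result (PCR or antigen test) within 8 days of screening" (criterion 3). No listed criterion excludes earlier infection. SAP 3.4 asks only for a negative PCR: "Modified FAS (mFAS) includes all FAS participants with a confirmed negative SARS-CoV-2 RT-PCR test at baseline".
- **Other covariates.** The imputation model in SAP 4.6.1 and the exploratory logistic model in SAP 4.6.3 have open-ended covariate lists. Serostatus could be added to either, but neither names it. SAP section 6 is not in the public text, so this describes the visible text only.

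**The concern.** The primary analysis set can contain people who already carry antibodies. If antibodies lower the risk of infection, part of the variation in the outcome has nothing to do with treatment. Chance imbalance in serostatus between arms then adds noise to a comparison that does not account for it. Stratifying by serostatus removes that variation at no extra data-collection cost.

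What is at stake is efficiency. The country-only test is not biased, holds its type I error, and meets its stated power on the plan's own assumptions.

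**Working it through.** **1. The plan's own figures.** Inputs from SAP 1.4: 54% versus 34% (a 20-point difference, as OR 2.28 confirms), two-sided 5%, 90% power, 30% non-evaluable.

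- OR = (0.54 × 0.66)/(0.46 × 0.34) = 2.28.
- A = [1.96√(2 × 0.44 × 0.56) + 1.2816√(0.54 × 0.46 + 0.34 × 0.66)]² = 5.094.
- Casagrande-Pike n = A[1 + √(1 + 4 × 0.20/A)]²/(4 × 0.20²) = 137.2, so 138 per arm, as stated.
- 138/0.70 = 197.1, so 198, rounded to 200, as stated. Conversely, 200 × 0.70 = 140 evaluable per arm.
- Simulated power of the planned test at 54% versus 34% is 92.2% at 140 per arm and 98.2% at 200.

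**2. Assumptions not in the documents.** Seroprevalence 10-20%. Placebo risk in seropositives 38, 27, 10 or 5%, which is about 30, 50, 80 or 90% below 54%. In the main frame, 54% is the placebo risk in seronegatives and the OR is 2.28 in both strata.

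**3. One cell by hand: 140 per arm, 20% seropositive, 5% placebo risk in seropositives.**

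- Ivermectin risk in seropositives: odds (0.05/0.95)/2.28 = 0.0231, risk 0.0226.
- Blended risks: placebo 0.8 × 0.54 + 0.2 × 0.05 = 0.442; ivermectin 0.8 × 0.34 + 0.2 × 0.0226 = 0.2765. The overall difference falls to 16.5 points.
- For stratum size n_s per arm, the CMH numerator has mean D = Σ n_s(p₀ − p₁)/2, null variance V = Σ n_s p̄(1 − p̄)/2 and true variance W = Σ n_s[p₀(1 − p₀) + p₁(1 − p₁)]/4. Power ≈ Φ[(D − 1.96√V)/√W].
- Stratified (112 seronegative and 28 seropositive per arm): D = 11.58, V = 14.29, W = 13.73, power 87.0%.
- Unstratified: the same formula on the blended risks gives 82.6%.

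Simulation gives 87.0% and 83.1%.

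**4. Full grid.** Simulated CMH without continuity correction, 200,000 trials per cell. Power (%) without → with serostatus at 140 per arm; the last two columns give the gain in points over 10-20% seropositive.

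| Lower risk in seropositives | 10% seropositive | 20% seropositive | Gain at 140 | Gain at 200 |
|---|---|---|---|---|
| 30% | 91.5 → 92.0 | 91.2 → 91.7 | 0.4-0.5 | 0.1-0.2 |
| 50% | 90.8 → 91.6 | 89.4 → 90.5 | 0.8-1.1 | 0.3-0.5 |
| about 80% | 88.8 → 90.4 | 85.0 → 88.0 | 1.7-3.0 | 0.8-1.7 |
| about 90% | 88.0 → 90.1 | 83.1 → 87.0 | 2.1-3.9 | 1.1-2.2 |

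Type I error is 4.8-5.2% unstratified and 4.9-5.1% stratified. At 170 per arm the gains for the four rows are about 0, 0.1-0.5, 0.8-2.5 and 1.1-3.4.

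**5. Sensitivity.**

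- *54% versus 34% held overall:* gains 0.4-3.8 at 140 and 0.1-1.1 at 200.
- *Only 3-5% seropositive:* 0.3-1.3 at 140 and 0.0-0.4 at 200.
- *No protection:* 0.1 and 0.0. At 140, about 0.1-0.2 of any gain arises because the unstratified test runs slightly below 5%.
- *Imperfect serology (85% sensitivity, 97% specificity, 10% missing):* for 50-90% lower risk, gains fall to 0.5-2.2 at 140 and 0.2-1.3 at 200.
- *Four unequal countries (50/30/15/5%):* gains within about 0.2 point of the table.
- *Multiple imputation (140 observed plus 30 imputed per arm, 10 imputations, Rubin's rules on the log Mantel-Haenszel OR):* gains 0.1-0.4, 0.5-1.2, 1.6-3.3 and 1.8-4.3 for the four rows; type I error 5.0-5.1%.

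No run combined imputation, misclassification and several countries.

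**The case against.** The strongest reply is that nothing is wrong. Stratifying the test by the randomisation factor is standard, and one more prognostic stratum is a matter of preference. That stands, and it is why this is only a suggestion.

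Further points:

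- **Frame.** SAP 1.4 applies 54% to the whole placebo group, not to seronegatives. On that reading the top gain at 200 per arm halves to 1.1 points, from about 98% power. This stands. The top gain at 140 hardly changes (3.8).
- **External inputs.** Every driver of the gain is assumed, and the upper ends need 20% seropositive together with about 90% lower risk. This stands; at 30-50% lower risk the main-frame gain is 0.4-1.1 points at 140 and 0.1-0.5 at 200.
- **Idealised serology and test discreteness.** Both shrink the gain. At 170 per arm with 30% lower risk it disappears.
- **Text not shown.** Serostatus may appear in parts of the SAP or full protocol that are not public. This cannot be excluded. In the visible text, the open covariate lists permit serostatus without pre-specifying it, and neither list belongs to the primary test.
- **Timing.** An interim analysis may already have closed the window for changing the primary test. The fix allows for that.

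None of this overturns the ranges or shows material harm from the added stratum.

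**Conclusion.** The point holds as an optional improvement. The planned test is valid and needs no correction, but it leaves unused a pre-treatment value that may be strongly prognostic.

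Under the assumed 10-20% seropositive and 30-90% lower risk, pre-specifying serostatus adds about 0.4-4 points of power at 140 evaluable per arm and about 0-2 at 200. The number that will count lies somewhere between: SAP 1.4 does not split the 30% by cause, and SAP 4.1.2 imputes participants who discontinue, so more than 140 per arm may contribute.

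Most of the fall in power below 92% in the table comes from the lower blended event rate, which stratifying does not cure. Confidence is medium, because seroprevalence and protection are both assumed.

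**What to change.** Amend the SAP as follows:

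- Stratify the primary CMH test and the Mantel-Haenszel risk difference by country and D1 serostatus. In a single-country study, use the serostatus-stratified CMH in place of the unadjusted test.
- Define seropositive by the assay's pre-specified positivity threshold, since the protocol records antibody levels. State a rule for missing serology, for example pooling with negative; a separate category changed power by no more than about 0.1 point.
- Name D1 serostatus as an imputation covariate, and keep the imputation split by stratification factor to country only.
- Keep the country-only CMH as a sensitivity analysis.
- Use the same strata in any interim efficacy test.

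Timing is the main constraint. SAP 2.1 places finalisation before an interim analysis and allows amendments after the DMC meeting; SAP 5 has an unblinded statistician working on the interim. Blinded staff should write the amendment, and it should be final before any unblinded interim result can inform it. If that is no longer possible, leave the country-only CMH as primary and report the serostatus-adjusted test as supportive.

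The other costs are small. The odds ratio becomes conditional on serostatus, some country-by-serostatus cells will be sparse, and missing or misclassified serology removes roughly a third to a half of the gain. No new data are needed. The protocol synopsis names the CMH test without fixing its strata, so the visible protocol text does not stand in the way; the full statistical section should be checked.

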4.6.2 Secondary endpoints

Statistical Analysis Plan	Version 1.0		Page 15 of 25
Sponsor	MedinCell	Protocol No	mdc-TTG-CT-002

The analysis of the secondary endpoints is purely explorative.

Results of RT-PCR tests and time to a positive test will be performed on the mFAS and PP population, while the analysis related to the occurrence of symptoms, (related) adverse events are performed on the FAS and PP population.

Treatment comparisons on proportions will be done using Cochran Mantel Haenszel chi-square test presenting odds-ratios, relative risk, and risk differences with 95% confidence intervals. Country will be used as a stratification factor. In case the study was only performed in one country, the Chi-squared/Fisher's exact test will be used.

Comparisons between treatment groups on time to events will be done by using a Cox proportional hazard model, under the assumption of proportional hazards. Time-to event curves will be created for visualization. Hazard ratios with 95% CI will be presented, together with the P-values. Censoring will be at study completion or at discontinuation date (including date of death, if occurring).

Treatment comparisons on mean score (WHO COVID-19 and NEWS-2) will be performed per time point by means of the t-test. If normality cannot be assumed based on visual inspection, a non-parametric alternative will be used.

Statistical Analysis Plan	Version 1.0		Page 16 of 25
Sponsor	MedinCell	Protocol No	mdc-TTG-CT-002

Treatment comparisons on durations will be examined by means of the non-parametric Wilcoxon-Rank-Sum test. If normality can be assumed based on visual inspection, a parametric alternative will be used.

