1.4 Planned sample size

The sample size was calculated to compare the proportion of participants who become positive to SARS-CoV-2 RT-PCR within 1 month after randomisation between the two groups: Placebo group and ivermectin group. The assumptions are based on results of a study assessing the transmission of SARS-CoV-2 infections in households carried out in the US between April and September 2020. Thus it is expected that the proportion of participants becoming infected in the placebo group is 54% or higher (Grijalva et al, 2020). Furthermore, a reduction by 20% is expected in the ivermectin group (OR=2.28).

When requiring a power of 90% (1- β) and a significance level of 5% (α), then according to the Casagrande & Pike formula the required sample size to detect such difference with a test of comparison of two proportions is equal to 138 participants per treatment arm (Casagrande et al, 1978).

A total of 396 participants (198 per arm), rounded up to 400 participants (200 per arm) is required to account for an estimated rate of randomised participants who won't be valued for the primary analysis of 30%.

[figure not shown]

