3.5 Per-protocol Set

The Per-Protocol Set (PPS) is a subset of participants in the mFAS who did not present major deviations from the trial protocol.

The primary efficacy endpoint will be analysed using the mFAS and the PP set. The PP analysis will be considered as a sensitivity analysis.

Secondary efficacy endpoints will be analysed using the FAS or mFAS and PP set.

In case of dispensation/randomisation major error (i.e. the participant did not receive the treatment planned by the randomisation), in agreement with the intention-to-treat (ITT) principle, participants in FAS and mFAS analyses will be analysed in the group planned by the randomisation and not "as treated". As treated analyses will be performed as sensitivity analyses only if the frequency of major dispensation/randomisation error is greater than 10%.

The safety set will be used for safety analyses. In case of dispensation/randomisation major error the safety analyses will be performed "as treated", according to the real treatment received by the participant.

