4 STATISTICAL ANALYSES

All statistical analyses will be performed using the SAS® software (Version 9.4 or later, SAS institute, North Carolina, USA).

All descriptive statistics will be given by treatment group. For baseline and basic variables, they will also be given for the entire analysis set. Screening failure data will not be analysed.

If not stated otherwise the following standard types of descriptive analyses will be presented:

- Descriptive statistics for continuous data

Statistical Analysis Plan	Version 1.0		Page 10 of 25
Sponsor	MedinCell	Protocol No	mdc-TTG-CT-002

N, mean, SD, min, lower quartile, median, upper quartile, and max will be presented. These descriptive statistics will be determined for measured values and optionally for differences to baseline.

Descriptive statistics for categorical data

Absolute frequencies and percentages will be presented. Percentage bases (denominators) will be identified in the table title or footnote (i.e. all subjects at risk, all cases). For changes from baseline, shift tables may be generated.

Inferential statistics

Unless otherwise stated, all statistical tests will be performed two-sided and at a type I error probability of α =0.05.

Unless otherwise stated, all confidence intervals (CIs) will be derived two-sided and at a confidence probability of $1-\alpha=0.95$.

Listings

All recorded data will be listed by subject sorted by treatment group. Identification variables are centre number, participant number and treatment.

Derived data will be stored in special analysis data sets and will be calculated as outlined in section 6.1.

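### The symptom and clinical-event analyses pair the FAS with a per-protocol set drawn from the mFAS, so the two differ in baseline infection as well as deviations, and no full-set prevention result is planned

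*SAP*

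**What the plan says.** Three definitions in SAP section 3 matter here.

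- The FAS (3.3) requires randomisation, at least one tablet and at least one later efficacy assessment. It sets no condition on the Day 1 PCR.
- The mFAS (3.4) "includes all FAS participants with a confirmed negative SARS-CoV-2 RT-PCR test at baseline".
- The PP set (3.5) "is a subset of participants in the mFAS who did not present major deviations".

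SAP 4.6.2 puts PCR results and time to a positive test on the mFAS and PP set, which is a matched pair. For the clinical endpoints it says that "the analysis related to the occurrence of symptoms, (related) adverse events are performed on the FAS and PP population". Country is the only stratification factor named. SAP 3.5 allows either the FAS or the mFAS for secondary endpoints in general, but 4.6.2 settles on the FAS for these. The same section calls the secondary analyses purely exploratory.

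Baseline PCR-positive people can be enrolled. In the protocol's Schedule of Assessments, footnote (e) makes a positive rapid antigen test a screen failure, and no such rule is attached to the Day 1 PCR. Footnote (d) continues PCR testing only in those confirmed negative at baseline, which presupposes that some will not be.

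**The concern.** The trial's primary objective is prevention. A participant infected before the first dose can show an early-treatment effect but not prevention of that infection. Pooling such participants with the uninfected gives one estimate for two questions, weighted by an unknown share.

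The second problem is how the pair of results will be read. A PP result beside a full-set result is normally taken to show the influence of deviations. Here, moving from the FAS to the PP set also removes everyone without a confirmed negative baseline PCR. A PP estimate further from the null than the FAS estimate could be misread as a benefit of adherence when it reflects only the change in baseline status. The set that would separate the two explanations, the mFAS, has no planned result for these endpoints.

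**Working it through.** **Comparing the sets.**

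| Endpoint group | Full set | PP set lies within | What changes from full set to PP |
|---|---|---|---|
| PCR result, time to positive test | mFAS | mFAS | major deviations |
| Symptoms, related clinical events | FAS | mFAS | major deviations and baseline PCR status |

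The mismatch follows from the definitions. It has an effect whenever the FAS contains anyone without a confirmed negative baseline PCR.

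**Reproducing the plan's figure.** SAP 1.4 expects that "the proportion of participants becoming infected in the placebo group is 54% or higher" and that "a reduction by 20% is expected in the ivermectin group (OR=2.28". With 54% versus 34%, the odds ratio is (0.54/0.46)/(0.34/0.66) = 2.28, so the 20% is an absolute difference. At two-sided 5% and 90% power, the continuity-corrected two-proportion formula gives 138 per arm. Then 138/0.70 = 197.1, that is 198 per arm, rounded to 200. These match the plan, and the present point does not affect them.

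**Inputs for the illustration.**

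- From SAP 1.4: infection risk 54% (placebo) versus 34% (ivermectin), applied to baseline negatives; 200 per arm.
- Assumed, because the documents do not give them: 60% of infections symptomatic; symptom risk s in baseline positives on placebo of 60% or 80%; share q of baseline positives of 2% to 30%; no treatment effect in baseline positives, varied below.

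**Baseline negatives.** 0.54 × 0.6 = 32.4% versus 0.34 × 0.6 = 20.4%. The difference is 12.0 points and the risk ratio (RR) 0.63.

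**FAS.** Risk = (1 − q) × risk in negatives + q × risk in positives. For q = 10% and s = 60%, placebo is 0.9 × 0.324 + 0.1 × 0.6 = 35.2%, ivermectin is 0.9 × 0.204 + 0.1 × 0.6 = 24.4%, and RR is 0.69.

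| q | s = 60%: risks, RR | s = 80%: risks, RR | Difference (points) |
|---|---|---|---|
| 2% | 33.0% vs 21.2%, 0.64 | 33.4% vs 21.6%, 0.65 | 11.8 |
| 5% | 33.8% vs 22.4%, 0.66 | 34.8% vs 23.4%, 0.67 | 11.4 |
| 10% | 35.2% vs 24.4%, 0.69 | 37.2% vs 26.4%, 0.71 | 10.8 |
| 20% | 37.9% vs 28.3%, 0.75 | 41.9% vs 32.3%, 0.77 | 9.6 |
| 30% | 40.7% vs 32.3%, 0.79 | 46.7% vs 38.3%, 0.82 | 8.4 |

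**Varying the effect in baseline positives.** If their RR is also 0.63, the FAS ivermectin risk is 0.63 times the FAS placebo risk for every q. The RR stays at 0.63 and the absolute difference grows (14.0 points at q = 20%, s = 60%). If their RR is 0.80, the FAS RR at q = 20% is 0.68–0.69.

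**Power** (two-sided 5%, 200 per arm in the FAS, 200 × (1 − q) in the mFAS, no other losses).

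- No effect in positives: FAS 64–66%, 51–53% and 40–42% at q = 10%, 20% and 30%, against 74%, 68% and 63% in the mFAS. At q = 2–5%, 71–76% against 76–77%.
- Equal RR of 0.63: FAS 82–95% over q = 10–30%, above the mFAS.

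**Does stratifying the FAS by baseline PCR remove the dilution?** When the arms are of equal size within each stratum, the Mantel-Haenszel RR is the sum of ivermectin events over the sum of placebo events, which is the unstratified RR. The values in the table therefore stand. Power with no effect in positives rises to about 68–70%, 57–60% and 45–50% at q = 10%, 20% and 30%, still below the mFAS.

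**The case against.** The FAS is a legitimate choice. It preserves the randomised comparison, and SAP section 1 lists collecting data on COVID-19 clinical outcomes as a separate aim. That stands, and the FAS analysis should stay.

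A reader might infer that pooling dilutes the prevention effect as a matter of fact. The documents do not support that. Dilution needs a weaker effect in those already infected, which is plausible but not established; with an equal RR there is none.

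A reader might also infer that baseline positives will supply much of the symptom data. No passage gives their number or symptom risk. Entry removes Day 1 antigen positives, anyone with a positive PCR or antigen result within 8 days of screening, and anyone with typical symptoms in the preceding 48 hours. The share may be small, and at 2–5% the shift in RR is slight.

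The illustration models any symptomatic infection. The plan's endpoints include severe symptoms, hospitalisation, death and score changes, so the power figures do not carry over to them. They also ignore losses, whereas SAP 1.4 allows for 30% not evaluable in the primary analysis.

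Finally, SAP 3.5 calls the PP analysis a sensitivity analysis directly after naming the primary endpoint, not explicitly for secondary ones. This softens the comparability point. It does not remove it, because 4.6.2 still reports the two sets side by side.

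**Conclusion.** The mismatch of sets holds on the text alone: for symptoms and related clinical events, FAS versus PP changes baseline infection status and deviations together, and no full-set result addresses prevention. The size of any dilution is conditional. With no effect in baseline positives, the RR moves from 0.63 to at most 0.67 with up to 5% baseline positive, and to 0.79–0.82 with 30%; with an equal relative effect it does not move. The share of baseline positives, their symptom risk and the effect in them are all assumptions.

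It would also be wrong to conclude that the missing baseline-PCR stratum is the cause, since adding it leaves the diluted RR where it is. The FAS analysis is not invalid, and the primary analysis, on the mFAS, is untouched. Because the secondary endpoints are exploratory, this is an improvement to consider rather than a required correction.

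**What to change.** In SAP 4.6.2, keep the FAS analysis and also report symptoms, COVID-19 related clinical events, hospitalisation and the WHO and NEWS-2 scores on the mFAS. Name the mFAS result as the prevention estimate and as the comparator for the PP set.

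In addition, show the FAS results separately by baseline RT-PCR status, and use that status with country as a stratum in the CMH and Cox analyses where event counts allow. State that this gains some precision and does not remove dilution.

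The Day 1 PCR is already collected, and SAP 2.1 already provides for an amendment before database lock and unblinding. The cost is a wording change and one more set of tables. Strata will be sparse for rare events such as hospitalisation and death, for which descriptive counts by baseline status may be all that is feasible.
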